12.3.	AMENDMENTS TO THE PROTOCOL	29
12.4.	DATA RECORDS.....	29
13.	PUBLICATION AND AGREEMENT	29
14.	INVESTIGATORS AGREEMENT	30
15.	REFERENCES	31
16.	APPENDIX A	32
	APPENDIX B	35

Braintree Laboratories, Inc.
Protocol Number BLI400-303

Confidential

CLINICAL PROTOCOL SUMMARY SHEET**STUDY TITLE:**

An Open Label Study of Chronic Use of BLI400 Laxative in Constipated Adults

PROTOCOL: BLI400-303**VERSION DATE:** 4-13-2016**IND NUMBER:** 118,906**OBJECTIVE:**

To evaluate the safety of chronic use of BLI400 Laxative in constipated adults.

STUDY DESIGN:

This is an open-label, multi-center study in constipated outpatients.

SUBJECTS:

Approximately 300 male or female adult subjects with a history of constipation will be enrolled in this study (including approximately 100 elderly subjects).

STUDY MEDICATIONS:

BLI400 Laxative (21 grams of Lactitol Monohydrate, NF)

DURATION OF TREATMENT

Subjects will take BLI400 laxative daily for 12 months (52 weeks). Participation in this study will last for approximately 54 weeks, including the 14 day follow up telephone call.

PRIMARY ENDPOINT

Safety will be analyzed through the use of adverse event and ECG data, and the comparison of chemistry, hematology, and urinalysis values as measured at baseline and at specific time points throughout the study.

1. INTRODUCTION

The present approaches to the treatment of chronic idiopathic constipation (CIC) are limited and for some patients there are significant drawbacks that have not been resolved. It would be desirable to provide a source of relief for constipation that would permit dosing adjustments to optimize efficacy and safety and that would be pleasant to consume to improve patient compliance. The treatment should not have the safety issues associated with oral phosphate laxatives, have an acceptable safety profile, and be effective in numerous types of constipation.

Braintree Laboratories, Inc. is investigating the use of a new chemical composition, BLI400 (Lactitol Monohydrate NF Powder for Reconstitution) as a treatment for adult constipation. Ample published literature with lactitol provides significant preclinical and clinical studies which support the safe and effective use of this GRAS-listed compound.

These reports indicate that the BLI400 lactitol composition has promise as a candidate for further development for the treatment of constipation, as reviewed herein.

BLI400 is a member of the pharmaceutical class of osmotic laxatives; specifically it is a non-absorbed, colonically metabolized sugar alcohol (polyol). Studies reviewed here indicate it provides relief from the symptoms of constipation by rapidly inducing a patient-controlled bowel movement. While lactitol appears to be minimally, if at all, absorbed in the small intestine, colonic microbes split lactitol into D-galactose and D-sorbitol, which are fermentable to organic acids including lactic, formic, propionic, butyric and acetic acids (as reviewed in [Patil et al, 1987](#)). The osmotic properties of the small organic molecules consistently point to their pharmacodynamic effects as dependent on water retention with the stool. Thus, BLI400 is a pro-drug of an essentially non-absorbed osmotic laxative. Lactitol is generally considered to be pharmacologically inert and is often referred to as a “prebiotic” with no specific receptor targets for its laxative action.

Rationale for Performing Research with the Investigational Product

Lactitol monohydrate, at a daily dose of 21 grams per day appears to be a safe and effective treatment for constipation, but it has not been studied and proven in clinical

Braintree Laboratories, Inc.
Protocol Number BLI400-303

[figure not shown]
Confidential

trials in the US. Lactitol appears to be a “prebiotic”, a substrate for colonic bacteria which convert it into osmotically active small molecules. Extensive published and non-published literature supports its safety and efficacy, but a Phase III clinical trial is required for its registration in the US. It is envisaged there will be one, multi-site, controlled study in patients with documented constipation and that the design will be similar to other studies that have led to the approval of laxatives, such as those for MiraLAX, NDA 22-015 and consistent with FDA’s recommendations for study endpoints in CIC trials.

Physical, Chemical, and Pharmaceutical Properties and Formulation

Lactitol is a simple monosaccharide sugar alcohol, a synthetic derivative of the milk sugar lactose that was discovered in the 1920s. It is a dry, free flowing powder, readily soluble in aqueous solutions. As shown by the structure diagrams, it is an analog of the disaccharide lactulose.

Lactitol

Lactulose

[figure not shown]

Table 1-1
Components of a Typical Single Dose of BLI400

Component	Amount (g)*
Lactitol monohydrate, NF	21

The product will be provided in multi-dose bottles with a measuring cap to deliver 10.5 grams of BLI400.

Braintree Laboratories, Inc.
Protocol Number BLI400-303

Confidential

Nonclinical Studies: Extensive nonclinical studies have been performed with lactitol as support for its registration and marketing in countries outside the US and are reviewed in detail in the BLI400 Investigators' Brochure. The studies have covered basic pharmacology, genotoxicity and mutagenicity, acute and chronic studies including carcinogenicity and reproductive toxicity. These studies were carried out in mice, rats, dogs and rabbits.

Pharmacology: Lactitol is not degraded by the galactosidase enzymes of the small intestine. However, colonic microflora degrade lactitol extensively in rats so that lactitol elevated the proportions of acetic acid and lowered proportions of butyric acid in the hindgut of rats. The osmotic effects of these organic acids appear to provide the pharmacodynamic basis for lactitol's laxative action. Increased output of moist feces was seen in all animal species studied in a dose-related manner. The highest doses tested caused frank diarrhea in some studies.

Metabolic Effects: In some studies, total serum cholesterol and triglycerides were reduced equally in rats fed diets containing 7% sorbitol or lactitol. By acidifying fecal contents, lactitol lowered ammonia levels in animal models of hepatic encephalopathy, perhaps as a result of production of the poorly absorbed ammonium ion that follows lowering the cecal pH. Rats fed a diet containing 5% of lactitol for two weeks displayed a significant increase of calcium absorption.

Toxicology Studies: Only weak edema ensued after lactitol application to intact skin, but erythema and edema emerged when it was applied to abraded skin. Rodents treated with lactitol had loose, frequent stools and cecal enlargement. This was often accompanied by decreased weight gain and increased water consumption. Clinical chemistry changes included changes in electrolyte levels, decreased cholesterol and alkaline phosphatase. Perhaps as compensation for the electrolyte changes that probably followed the diarrhea, adrenal weight and hypertrophy of the zona fasciculata were seen in the highest dose groups. Renal tubular degeneration with nephrocalcinosis was occasionally seen and may follow the increased calcium absorption. Lactitol was not considered positive for mutagenicity or chromosomal damage studied in standard in vitro and in vivo assays. Life-long carcinogenicity studies have indicated that Leydig cell dysplasia occurred in

rats at high lactitol doses, but this was not seen in mice dosed for 24 months or dogs dosed for 12 months. This species-specific effect in some rat strains was not considered significant to humans, since ordinary milk sugar, lactose, produces a similar effect in rodents.

A minimal effective dose of 0.25 g/kg has been suggested, and most studies have found that a starting dose of 20 g of lactitol is effective and produces minimal side effects. Some studies that have allowed the subjects to make dosage increases to achieve relief of constipation symptoms and dose reductions to minimize side effects have indicated that this strategy can optimize therapy.

[Maydeo \(2010\)](#) presented a systematic review of six published randomized, non-randomized and open trials comparing the safety and efficacy of lactitol to those of lactulose. Overall, lactitol was comparable to lactulose in efficacy measures (normal stool consistency and number of bowel movement per week). Patients found lactitol to be more acceptable and were more compliant with it largely due to its superior palatability (73.2 % vs. 26.8 %). Lactitol was significantly better than lactulose in the frequency of adverse events (31.2 ± 0.8 % vs. 62.1 ± 1.1 %, $p= 0.0019$). The physicians' assessment favored lactitol as compared to lactulose (61.91% vs. 47.83%). The following table is adapted from Maydeo's summary of the reviewed trials.

Parameter Evaluated	Lactitol	Lactulose
Patient's acceptance	73.2%	26.8%
Consistency of stool (normal/soft)	$80.5 \pm 4.5\%$	$75.0 \pm 8.0\%$
Bowel movement/week	5.9 ± 0.2	5.6 ± 0.6
Incidence of side-effects	31.2 ± 0.8	$62.1 \pm 1.1\%$
Global efficacy judged by physicians	61.9%	47.8%

2. STUDY OBJECTIVE

To evaluate the safety of chronic use of BLI400 laxative in constipated adults.

3. STUDY PLAN

3.1. Study Design

This is an open-label, multi-center study in which constipated subjects will receive BLI400 for 12 months.

3.2. Number of Subjects

Approximately 300 constipated subjects will be enrolled into this study, including approximately 100 elderly subjects (≥ 65 years of age at Visit 1).

3.3. Duration of Study

Qualifying subjects will receive BLI400 at Visit 1 and will begin a 12-month Treatment Period. Subjects will return for clinic visits at the end of Months 2, 4, 6, 9 and 12. A follow up call will take place 2 weeks after the end of treatment. A completed subject is defined as a subject that completes the Visit 6 (Month 12) visit.

3.4. Study Treatments

BLI400 Laxative

BLI400 laxative will be provided polyethylene bottles containing sufficient study medication for 30 days of dosing. The bottles will be equipped with a cap that can be used to measure 10.5 grams of BLI400. Each bottle will also have a clinical label containing a caution statement, study code, study sponsor and subject number. Subjects will be instructed to mix the contents of 2 capfuls (approximately 21 g) in 4 - 8 oz of juice or other beverage, and take once daily preferably in the morning. Subjects that develop persistent diarrhea or loose stools will be allowed to adjust their dose down to 10.5g (1 capful) per day.

Rescue Bisacodyl

Subjects will be dispensed bisacodyl at each study visit (previously dispensed bisacodyl may be redispensed if needed, although this is not encouraged). Subjects will be instructed to take 5 – 10mg (1 – 2 tablets) of bisacodyl if they are experiencing severe discomfort due to their constipation, or have not had a BM in 4 days. No more than 6 tablets (30mg) of bisacodyl should be taken in a week.

If a subject does not have a bowel movement within 24 hours of taking a bisacodyl dose, a second dose should be taken. If after the second bisacodyl dose the subject does not have a BM within 24 hours, the subject should contact the site. The investigator should then consider having the subject return for an evaluation and/or discontinuing the subject from the study.

All study medication is required to remain at room temperature 20°-25°C (68°-77°F); excursions permitted between 15°-30°C (59°-86°F).

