4.1. Visit 1 (Day 0)

At the screening visit, the following procedures will be undertaken:

- Subject is fully informed about the study and gives written agreement to study participation in the form of a signed informed consent form (refer to [Section 4.1.1](#))
- Assess eligibility (refer to [inclusion/exclusion criteria](#))
- Review of medications
- Medical history including history of constipation (ROME criteria – See [Inclusion #2](#))
- Physical examination
- Vital signs, including assessment of orthostatic hypotension (while seated and after standing for a minimum of 2 minutes) including height and bodyweight, pulse and temperature
- A 12-lead ECG will be performed by qualified, trained site personnel. ECG output must be reviewed by a physician investigator. Any clinically significant cardiac abnormalities identified on the ECG should disqualify a subject. Data from the ECG will be collected in the eCRF.
- Urine pregnancy test (if applicable)
- Blood and urine samples will be collected for testing at a central laboratory, as shown below.

Chemistry: alkaline phosphatase, ALT, anion gap, AST, bicarbonate, blood urea nitrogen (BUN), calcium, chloride, creatine kinase, creatinine, eGFR, GGT, HCG, inorganic phosphate, magnesium, osmolality, potassium, sodium, uric acid. CK-MB will be tested in samples where the CK value is greater than 2.5 times the upper normal limit.

Hematology: hematocrit, hemoglobin, platelets count, red blood cell count, white blood cell count (and differentials)

Urinalysis: including electrolytes (sodium, potassium, magnesium, calcium), microscopic analysis, urine osmolality

Subjects with clinically significant laboratory abnormalities, deemed as a potential safety issue by the Investigator, may be discontinued at the Investigator's discretion.

If the subject is eligible for the study, assign a subject number.

Braintree Laboratories, Inc.
Protocol Number BLI400-303

Confidential

- Subjects will complete the Patient Assessment of Constipation Quality of Life questionnaire (PAC-QOL, refer to [Appendix A](#)) and the Patient Assessment of Constipation Symptom questionnaire (PAC-SYM, refer to [Appendix B](#))
- Dispense 2 bottles of BLI400
- Dispense rescue bisacodyl. Subjects will be allowed to take 5 – 10mg of bisacodyl if they are experiencing severe discomfort due to their constipation, or have not had a BM in 4 days.
- Instruct subject to maintain their normal dietary habits during study participation

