9. DATA ANALYSIS

9.1. Sample Size

Consistent with *ICH E1A Guideline for Industry, the Extent of Population Exposure to Assess Clinical Safety: for Drugs Intended for Long-term Treatment of Non-Life-Threatening Conditions (March 1995)*, 300 subjects will be treated with BLI400 for 12 months. This will allow for detection of adverse events that may increase in frequency or severity over time.

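### Section 3.4 can call for a second rescue dose that its own weekly cap forbids, and its only rescue-related site-contact step assumes that dose was taken

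*Combined protocol and SAP*

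**What the plan says.** The rescue rules are in Section 3.4 and read the same in both copies of the protocol in the combined document.

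- Dose and first trigger: "Subjects will be instructed to take 5 – 10mg (1 – 2 tablets) of bisacodyl if they are experiencing severe discomfort due to their constipation".
- Second trigger: four days without a bowel movement. Either trigger is enough.
- Weekly cap: "No more than 6 tablets (30mg) of bisacodyl should be taken in a week".
- Repeat dose: "If a subject does not have a bowel movement within 24 hours of taking a bisacodyl dose, a second dose should be taken". Its size is not given and the cap is not mentioned.
- Site contact: "If after the second bisacodyl dose the subject does not have a BM within 24 hours, the subject should contact the site". The investigator then considers an evaluation visit, discontinuation, or both.

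Section 4.1 (Visit 1, the dispensing step) repeats the dose range and both triggers ("Subjects will be allowed to take 5 – 10mg of bisacodyl if they are experiencing severe discomfort due to their constipation") but gives neither the cap nor the repeat-dose rule. Nothing ranks the cap against the repeat dose, and nothing says whether the week is rolling or calendar.

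**The concern.** Each rule is clear alone. Together, the cap can remove the dose that the repeat rule calls for. Site contact is worded as the step after that dose, so a subject who respects the cap does not meet its condition at the time the protocol seems to intend.

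The subjects in this position are those for whom study treatment is not working. Section 4.5 bars other laxatives until after Visit 6, and the clinic visits in Section 3.3 are two to three months apart. Such a subject must either exceed a stated limit or wait, with no rescue instruction for the wait. That is a safety follow-up matter in a study whose sole objective is safety.

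**Working it through.** **Inputs, all from Section 3.4:** 1–2 tablets (5–10 mg) per dose; cap 6 tablets (30 mg) per week; second dose due 24 h after a dose without a bowel movement (BM); triggers are severe discomfort (no waiting time) or 4 days (96 h) without a BM. One week = 168 h.

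**1. The plan's own figure.** Tablet strength = 10 mg / 2 = 5 mg. Cap = 6 × 5 mg = 30 mg, as stated.

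**2. One episode of two doses.** 2 to 4 tablets. It never reaches the cap.

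**3. Two episodes of two doses each.** Four doses of 1 or 2 tablets give 2^4 = 16 combinations.

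| Total tablets | Combinations | Against the cap of 6 |
|---|---|---|
| 4 | 1 | within |
| 5 | 4 | within |
| 6 | 6 | within |
| 7 (35 mg) | 4 | over by 1 tablet, 1/6 = 17% |
| 8 (40 mg) | 1 | over by 2 tablets, 2/6 = 33% |

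So 11 fit and 5 exceed. In three of the five (1+2+2+2, 2+1+2+2, 2+2+1+2) one tablet remains before the fourth dose, so a one-tablet dose would still fit arithmetically. In the other two, the first three doses are all 10 mg: 6 − (2 + 2 + 2) = 0 tablets remain, and a second dose of any permitted size breaks the cap. That is the unavoidable collision in a two-episode week.

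Three two-dose episodes would exceed the cap in 63 of 64 combinations. They fit into one week only through the discomfort trigger, because the 4-day trigger spaces episodes too widely.

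**4. How long the second dose is blocked.** Let the first dose be at 0 h and the third, which uses the last tablet and opens the second episode, at t h. The second dose of that episode is due at t + 24. On a rolling week the first tablets leave the count at 168 h. So:

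delay = 168 − (t + 24) = 144 − t hours.

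- *4-day trigger only.* Doses at 0 and 24 h, BM x hours after the second (0 < x < 24), next trigger at t = 24 + x + 96 = 120 + x. The second dose is due at 144 + x, always before 168 h. Delay = 24 − x, under a day. With x = 1 it is 23 h.
- *Severe-discomfort trigger.* Doses at 0 and 24 h, BM before 48 h, third dose at t = 48. The second dose is due at 72 h. Delay = 144 − 48 = 96 h, or 4 days.

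On a calendar week containing these doses, the count resets no later than 168 h after the first dose, so the delay is no longer than shown. Site contact falls 24 h after a failed second dose, so it moves back by the same delay. This assumes that the subject takes the postponed dose once tablets are free, which the text does not say.

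**5. Other routes to the site.** Section 4.2.1 tells subjects to contact the center for diarrhea or loose stools, not for absence of a BM. Section 5.1 asks for prompt reporting of adverse events in general. Neither says what to do on reaching the cap.

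**The case against.** The best reply is that a maximum printed beside a dosing instruction is normally read as limiting it, and that the rules can usually be followed together: the second dose has no fixed size, most two-episode combinations fit, and one episode always does. This stands as a limit on scope. It does not remove the problem, because after three 10 mg doses no permitted size fits, and reading the cap as overriding is what leaves the subject without a next step.

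There are also general safeguards. Adverse events are to be reported promptly (Section 5.1), bisacodyl is counted or reviewed at every follow-up visit (Sections 4.2.2 to 4.2.6), and the investigator may withdraw a subject (Section 8.2). These soften the consequence, but none is tied to reaching the cap.

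Four stronger readings are tempting, and the documents do not support them:

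- *The rescue rules contradict each other in general.* They collide only at the cap.
- *A subject who obeys the cap never reaches the site.* Tablets become available again as the week passes. The result is a delay without instruction, under a day on the 4-day trigger.
- *Section 4.1 contradicts Section 3.4.* It is shorter but consistent. Section 4.1.3 says that subjects receive instructions on rescue use; that material is not in the documents, so how it presents the cap cannot be judged.
- *Rescue or discontinuation results become inconsistent between sites.* No analysis in Sections 9.2 to 9.3.3 uses rescue consumption or discontinuation for lack of effect. The per-protocol set in Section 9.4.2 is supportive only, and the plan does not list rescue use among its exclusions.

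**Conclusion.** The concern holds as a conflict in the rescue instructions. It arises when a subject has used 6 tablets within a week, the last dose opened an episode, and no BM follows within 24 hours. The text does not say which rule prevails, and a subject who keeps to the cap has site contact delayed with no instruction in the meantime.

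The delay is under a day when only the 4-day trigger operates and about 4 days for doses at 0, 24 and 48 h. The second figure belongs to that schedule: the discomfort trigger has no minimum interval, so other spacings give other delays. A subject who follows the repeat rule instead takes 7 or 8 tablets (35 or 40 mg) against 6 (30 mg).

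The conflict is confined to repeated use within a week and, with two episodes, to doses near the top of the 5–10 mg range. The documents give no basis for estimating how often it would occur. Sample size and the planned analyses are untouched. It is worth correcting because it concerns safety follow-up and the correction is cheap.

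**What to change.** The sponsor should reconcile the cap, second-dose and site-contact sentences in Section 3.4 so that the text states:

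- which instruction prevails when the cap and the second dose collide;
- whether the week is rolling or calendar;
- a site-contact step worded so that a subject stopped by the cap can still reach it.

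The reconciled text should then be carried into Section 4.1 and the instructions given to subjects, so that the dispensing step and the full rule agree. The clinical content is for the sponsor to decide; no dose or rule is proposed here.

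The cost is a wording amendment, with the IRB approval that Section 12.3 requires, and possibly a few more calls to sites. No procedure, visit or analysis changes.

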3.5. Subject Selection

3.5.1. Inclusion Criteria

Subjects will be admitted to the study if they are:

1. Male or female subjects at least 18 years of age
2. Constipated, defined by the following adapted ROME II definition ([Drossman et al, 2000](#)):
 - A. Fewer than 3 spontaneous defecations per week and at least one of the following symptoms for at least 12 weeks (which need not be consecutive) in the preceding 12 months:
 - a. Straining during > 25% of defecations
 - b. Lumpy or hard stools in > 25% of defecations
 - c. Sensation of incomplete evacuation for > 25% of defecations
3. If female, and of child-bearing potential, is using an acceptable form of birth control (hormonal birth control, IUD, double-barrier method, depot contraceptive, sterilized, abstinent, or vasectomized spouse)
4. Negative urine pregnancy test at screening, if applicable
5. In the Investigator's judgment, subject is mentally competent to provide informed consent to participate in the study

3.5.2. Exclusion Criteria

Subjects who meet any of the following criteria will be excluded from the study:

1. Report loose (mushy) or water stools in the absence of laxative use for more than 25% of BMs during the 12 weeks before Visit 1
2. Meet the Rome II criteria for Irritable Bowel Syndrome: reports abdominal discomfort or pain that has two or more of the following three features for at least 12 weeks, which need not be consecutive, in the 12 months before Visit 1:
 - Relieved with defecation
 - Onset associated with a change in frequency of stool
 - Onset associated with a change in form (appearance of stool)
3. Subjects with known or suspected ileus, gastrointestinal obstruction, gastric retention, bowel perforation, toxic colitis, toxic megacolon
4. Subjects who have had major surgery 30 days before Visit 1; appendectomy or cholecystectomy 60 days before Visit 1; abdominal, pelvic, or retroperitoneal surgery 6 months before Visit 1; bariatric surgery or surgery to remove a segment of the GI tract at any time before Visit 1
5. Subjects with hypothyroidism that is being treated and for which the dose of thyroid hormone has not been stable for at least 6 weeks at the time of Visit 1
6. Subjects taking laxatives, enemas or prokinetic agents that refuse to discontinue these treatments from Visit 1 until after completion of Visit 6
7. Subjects who are pregnant or lactating, or intend to become pregnant during the study
8. Subjects of childbearing potential who refuse a pregnancy test
9. Subjects who are allergic to any BLI400 component (lactitol)
10. Subjects taking narcotic analgesics or other medications known to cause constipation.
11. Subjects with clinically significant cardiac abnormalities identified at the Visit 1 ECG
12. Subjects with clinically significant laboratory abnormalities, deemed as a potential safety issue by the Investigator, may be discontinued at the Investigator's discretion.
13. Subjects who, in the opinion of the Investigator, should not be included in the study for any reason, including inability to follow study procedures
14. Subjects who have participated in an investigational clinical, surgical, drug, or device study within the past 30 days
15. Subjects with an active history of drug or alcohol abuse
16. Subjects have been hospitalized for a psychiatric condition or have made a suicide attempt during the 2 years before Visit 1
17. Subjects who withdraw consent at any time prior to completion of Visit 1 procedures

